## 4.4.3. Secondary and Exploratory Endpoints

Table GPHZ.4.2. Secondary and Exploratory Efficacy Measures for Improvement of Obesity-related Health Problems

Analysis variable	Criteria/Measures	Analysis set	Analysis method	Additional Information
Percentage of participants who met the following criteria at 72 weeks from BL	Improvement in at least 2 obesity related health problems for participants with BL BMI >27 and <35 kg/ m², or Improvement in at least 1 obesity related health problem for participants with BL BMI >35 kg/ m²	Efficacy analysis set	Logistic model in Section 4.4.2.2	Definition of endpoint: 4.4.1.3
	Improvement in at least 2 obesity-related health problems	Efficacy analysis set - participants with BL BMI ≥27 and <35 kg/m²	Logistic model in Section 4.4.2.2	Exploratory
	Improvement in at least 1 obesity-related health problem	Efficacy analysis set - participants with BL BMI ≥35 kg/m 	Logistic model in Section 4.4.2.2	Exploratory
Improvement in laboratory tests for obesity-related health problems (72 weeks)	Mean changes in OGTT 2-hr glucose at 72 weeks from BL	Efficacy analysis set - participants with IGT at BL	MMRM model in Section 4.3.2.1	
	Mean changes in fasting glucose at 72 weeks from BL	Efficacy analysis set - participants with IGT at BL	MMRM model in Section 4.3.2.1	
	Mean changes in Fasting lipids (TG) at 72 weeks from BL	Efficacy analysis set - participants with hyperlipidemia at BL	MMRM model in Section 4.3.2.1	
	Mean changes in HFF at 72 weeks from BL	Efficacy analysis set - participants diagnosed as NAFLD by MRI at BL	ANCOVA model in Section 4.4.2.1	
Improvement of IGT (72 weeks)	Proportion of participants who achieved improvements of IGT	Efficacy analysis set - participants with IGT at BL	Logistic model in Section 4.3.2.2	

Analysis variable	Criteria/Measures	Analysis set	Analysis method	Additional Information
Improvement of hyperlipidemia (72 weeks)	Proportion of participants who achieved improvements of hyperlipidemia	Efficacy analysis set - participants with hyperlipidemia at BL	Longitudinal logistic model in Section 4.4.2.3	
Improvement of NAFLD (72 weeks)	Proportion of participants who achieved improvements of NAFLD	Efficacy analysis set - participants diagnosed as NAFLD by MRI at BL	Logistic model in Section 4.3.2.2	Compare TZP 10 mg, 15 mg and pooled TZP doses with placebo
Percentage of participants who met the following criteria at 72 weeks from BL	Improvement in at 2 or 3 obesity related health problems	Efficacy analysis set - participants with 3 defined obesity-related health problems	Logistic model in Section 4.3.2.2	Exploratory
	Improvement in at 2 obesity related health problems	Efficacy analysis set - participants with 2 defined obesity-related health problems	Logistic model in Section 4.3.2.2	Exploratory
	Improvement in at 1 obesity related health problems	Efficacy analysis set - participants with 3 defined obesity-related health problems	Logistic model in Section 4.3.2.2	Exploratory

Abbreviations: ANCOVA = analysis of covariance; BL = baseline; BMI = body mass index; IGT = impaired glucose tolerance; MMRM = mixed model for repeated measures; NAFLD = non-alcoholic fatty liver disease; OGTT = oral glucose tolerance test; TG = triglycerides; TZP = tirzepatide.

Table GPHZ.4.3. Secondary and Exploratory Efficacy Measures for Body Mass

Analysis variable	Criteria/Measures	Analysis set	Analysis method	Additional Information
Change in body weight (24, 52, and 72 weeks)	Proportion of participants who achieve the following criteria from BL	Efficacy analysis set	Logistic model in Section 4.3.2.2	
	
 
≥5% body weight reduction (only at 24 and 52 weeks)
 
≥7% body weight reduction
 
≥10% body weight reduction
 
≥15% body weight reduction
 
≥20% body weight reduction
 
			
	Mean percent change from BL in  • Body weight (%) (Only at 24 and 52 weeks)	Efficacy analysis set	MMRM model in Section 4.3.2.1	
	Mean change from BL in			
	

Absolute body weight (kg)

BMI

			
EWL	EWL defined in Section 4.4.1.1	Efficacy analysis set	MMRM model in Section 4.3.2.1	
Change in VAT and SAT (72 weeks)	Mean change from BL in  VAT area (cm²)  SAT area (cm²)  VAT/SAT ratio	Efficacy analysis set	ANCOVA model in Section 4.4.2.1	
	Mean percent change from BL in  VAT area (cm²)  SAT area (cm²)  VAT/SAT ratio	Efficacy analysis set	ANCOVA model in Section 4.4.2.1	

Analysis variable	Criteria/Measures	Analysis set	Analysis method	Additional Information
	Proportion of participants who achieve VAT <100 cm 	Efficacy analysis set - participants with VAT ≥100 cm² at	Logistic model in Section 4.4.2.2	
Change in waist circumference (24, 52, and 72 weeks)	Mean change from BL in waist circumference	BL Efficacy analysis set	MMRM model in Section 4.3.2.1	

Abbreviations: ANCOVA = analysis of covariance; BL = baseline; BMI = body mass index; EWL = excess weight loss; MMRM = mixed model for repeated measures; SAT = subcutaneous adipose tissue; VAT = visceral adipose tissue.

Table GPHZ.4.4. Secondary and Exploratory Efficacy Measures for IGT, Hyperlipidemia, NAFLD and Other Parameters

Analysis variable	Criteria/Measures	Analysis set	Analysis method	Additional Information
Change in IGT related parameters (24, 52, and 72 weeks)	Mean change from BL in  Fasting glucose HbA1c Fasting insulin C-peptide HOMA2-%B HOMA2-%S Matsuda Index Insulin Secretion Beta-cell function	(1)Efficacy analysis set; (2) Efficacy analysis set - participants with IGT at BL; (3) Efficacy analysis set - participants with normoglycemic at BL	MMRM model in Section 4.3.2.1	
Change in hyperlipidemia related parameters (24, 52, and 72 weeks)	Mean change from BL in  TG TC VLDL-C LDL-C (direct) HDL-C Non-HDL-C FFA	(1) Efficacy analysis set - participants with hyperlipidemia at BL; (2) Efficacy analysis set	MMRM model in Section 4.3.2.1	
Change in NAFLD related parameters (24, 52, and 72 weeks)	Mean change from BL in  ALT  AST  GGT  AST/ALT ratio  K-18 (M30)  Pro C3  ELF  FIB-4 index	(1) Efficacy analysis set; (2) Efficacy analysis set - participants with NAFLD at BL	MMRM model in Section 4.3.2.1	

Analysis variable	Criteria/Measures	Analysis set	Analysis method	Additional Information
Change in blood pressure (24, 52, and 72 weeks)	Mean change from BL in     Systolic blood pressure     Diastolic blood pressure	Efficacy analysis set	MMRM model in Section 4.3.2.1	
Change in uric acid (24, 52, and 72 weeks)	Mean change from BL in  • Uric acid	Efficacy analysis set	MMRM model in Section 4.3.2.1	
Change in laboratory tests (24, 52, and 72 weeks)	Mean change from BL in  • Adiponectin (high molecular weight and total)  • Leptin  • hs-CRP  • TNFα  • eGFR  • Urinary albumin/creatinine ratio	Efficacy analysis set	MMRM model in Section 4.3.2.1	Exploratory objective
Time to onset of T2DM during 72 week treatment period	Onset of T2DM during 72 week treatment period from BL	Safety analysis set - participants with IGT at BL	Kaplan Meier plot will be used for estimation of survival rates over time Log-rank test will be used to compare survival curves	Exploratory objective To compare TZP 10 mg, 15mg and pooled TZP doses with placebo for participants with IGT at BL
Change in eGFR	Mean change from BL in • eGFR	Efficacy analysis set	MMRM model in Section 4.3.2.1	Exploratory objective added to protocol planned analyses

Analysis variable	Criteria/Measures	Analysis set	Analysis method	Additional Information
Shift in eGFR	Shift table of minimum baseline to minimum postbaseline	Efficacy analysis set		Exploratory objective added to protocol planned analyses
Change in UACR	Mean change from BL in UACR	Efficacy analysis set	MMRM model in Section 4.3.2.1	Exploratory objective added to protocol planned analyses
Improvement of hyperuricemia (72 weeks)	Proportion of participants who achieved improvements of hyperuricemia. Definition of improvement of hyperuricemia: Uric acid 7 mg/dL	Efficacy analysis set – participants with hyperuricemia at BL defined as uric acid > 7 mg/dL	Longitudinal logistic model in Section 4.4.2.3	Exploratory objective added to protocol planned analyses
Improvement of hypertension (72 weeks)	Proportion of participants who achieved improvements of hypertension. Definition of improvement of hypertension: Diastolic blood pressure <80 mmHg or Systolic blood pressure <130 mmHg.	Efficacy analysis set – participants with hypertension at BL defined as diastolic blood pressure ≥80 mmHg or Systolic blood pressure ≥130 mmHg.	Logistic model in Section 4.4.2.2	Exploratory objective added to protocol planned analyses
Change in NAFLD related parameters (24, 52, and 72 weeks)	Mean change from BL in  NAFLD fibrosis score	(1) Efficacy analysis set; (2) Efficacy analysis set - participants with NAFLD at BL	MMRM model in Section 4.3.2.1	Exploratory objective added to protocol planned analyses

Abbreviations: ALT = alanine aminotransferase; AST = aspartate aminotransferase; BL = baseline; eGFR = estimated glomerular filtration rate; ELF = enhanced liver fibrosis; FFA = free fatty acid; FIB-4 = Fibrosis-4; GGT = gamma-glutamyl transferase; HbA1c = glycated hemoglobin; HDL-C = high-density lipoprotein cholesterol; HOMA2-%B = homeostasis model assessment estimates steady state beta cell function; HOMA2-%S = homeostasis model assessment estimates steady state insulin sensitivity; hs-CRP = high-sensitivity C-reactive protein; IGT = impaired glucose tolerance; K-18 (M30) = keratin-18 M30 fragment; LDL-C = low-density lipoprotein cholesterol; MMRM = mixed model for repeated measures; NAFLD = non-alcoholic fatty liver disease; Pro-C3 = a fragment of the NH2-terminal propeptide of type III procollagen; T2DM = type 2 diabetes mellitus; TC = total cholesterol; TG = triglycerides; TNFα = tumor necrosis factor alpha; TZP = tirzepatide; UACR = urine albumin-to-creatinine ratio; VLDL = very low-density lipoproteins.

Unless otherwise stated, the assessment of secondary efficacy objective will be guided by the "efficacy" estimand, using the same population as for primary analysis.

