Study GPHZ is a Phase 3, multicenter, randomized, placebo-controlled, double-blinded study to evaluate the safety and efficacy of tirzepatide 10 mg and 15 mg administered subcutaneously once weekly compared with placebo when used in conjunction with a reduced-calorie diet and increased physical activity for weight management, in participants who have

- \cdot A BMI of 27 kg/m² or greater and less than 35 kg/m² and at least 2 obesity-related health problems; OR
- · A BMI of 35 kg/m² or greater and at least 1 obesity-related health problem.

Obesity-related health problems are defined as IGT, hyperlipidemia, or NAFLD.

All participants will undergo a 4-week screening period and a 72-week treatment period including a 20-week dose escalation. The safety follow-up period will be 4 weeks.

Study participants will be randomized in a 1:1:1 ratio to tirzepatide 10 mg QW, tirzepatide 15 mg QW, or placebo QW, stratified by

- baseline IGT (yes or no)
- baseline hyperlipidemia (yes or no)
- baseline NAFLD (yes or no), and
- sex (male, female).

Disclosure Statement:

This is a parallel group-treatment study with 3 arms that is participant- and investigator-blinded.

[figure not shown]
Number of Participants:

Approximately 348 participants will be screened to achieve 261 randomly assigned to study intervention for an estimated total of 87 evaluable participants per intervention group.

Intervention Groups and Duration:

All doses will be subcutaneously administered once-weekly using single-use pens. The starting dose of tirzepatide will be 2.5 mg QW (or matching placebo) for 4 weeks, then the dose will be increased by 2.5 mg (or matching placebo) every 4 weeks: 2.5 to 5 to 7.5 to 10 mg for those randomized to 10 mg, and continuing to 12.5 to 15 mg for those randomized to 15 mg.

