8.1.3. Exploratory Efficacy Assessments

The following exploratory assessment will be collected at the times shown in the Schedule of Activities (Section 1.3).

Obesity-related health problems

- Proportion of participants who achieved the following improvements of obesity-related health problems at 72 weeks regardless of BMI at baseline;
 - o Achieved improvement in ≥2 obesity-related health problems for participants with baseline BMI ≥27 and <35 kg/m²
 - o Achieved improvement in ≥1 obesity-related health problems for participants with baseline BMI ≥35 kg/m²
 - Achieved 2 or 3 improvements (only for participants with 3 defined obesity-related health problems) regardless of BMI at baseline
 - Achieved 2 improvements (only for participants with 2 defined obesity-related health problems regardless of BMI at baseline)
 - Achieved 1 improvement (only for participants with 1 defined obesity-related health problem regardless of BMI at baseline)

Other parameters

- Adiponectin (μg/mL) (both high molecular weight and total adiponectin, measured at central laboratory)
- Leptin (pg/mL) (measured at central laboratory)
- high-sensitivity C-reactive protein (hsCRP) (ng/dL) (measured at central laboratory)
- TNF-α (pg/mL) (measured at central laboratory)
- eGFR (mL/min/1.73 cm²) (creatinine measured at central laboratory) calculated using the Japanese Society of Nephrology formula: 194 × Cr 1.094 × Age 0.287 [if female; × 0.739]
- Urinary albumin/creatinine ratio (mg/gCre) (measured at central laboratory)

Incident Diabetes

- Time to onset of T2DM during the 72-week treatment period
 - o Definition and Management of Incident Diabetes

Definition of incident diabetes

Incident diabetes is followed by Japanese Clinical Practice Guideline for Diabetes 2019 (Araki et al. 2020) and defined when any 1 of the following occur after randomization:

- unequivocal hyperglycemia (random glucose ≥200 mg/dL) with signs or symptoms of hyperglycemia (e.g., dry mouth, polyposia, polyuria, body weight loss, or diabetic retinopathy).
- within a 4-week period, the following laboratory evidence of diabetic type criteria including either HbA1c ≥6.5%, or glucose levels (fasting glucose or OGTT 0-hour glucose ≥126 mg/dL and/or OGTT 2-hour glucose ≥200 mg/dL) are observed:
 - i. Both glucose level and HbA1c meets diabetic type criteria

- ii. Only glucose level meets diabetic type criteria
 - With typical symptoms of DM or definite diabetic retinopathy

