o Improvement in obesity-related health problems at 72 weeks	
 
Proportion of participants who met the following criteria at 72 weeks from BL
 
improvement in ≥2 obesity-related health problems for participants with BL BMI ≥27 and <35 kg/m²
 
improvement in ≥1 obesity-related health problems for participants with BL BMI ≥35 kg/m²
 
	
	
 
Proportion of participants who achieved the following number of improvements of obesity-related health problems regardless of BMI at BL
 
Achieved 2 or 3 improvements (only for participants with 3 defined obesity-related health problems)
 
Achieved 2 improvements (only for participants with 2 defined obesity-related health problems)
 
Achieved 1 improvement (only for participants with 1 defined obesity-related health problems)
 
	
IGT related parameters (all participants)		
o Change in OGTT (24, 52, and 72 weeks)	Mean change from BL in     OGTT 2-hr glucose     fasting glucose     insulin     C-peptide	
Hyperlipidemia related parameters (all participants)		

 
Change in fasting lipids (24, 52, and 72 weeks)
 
	Mean change from BL in  TG  TC  VLDL-C  LDL-C (direct)  HDL-C  non-HDL-C  FFA	

Objectives	Endpoints
Other parameters	
Change in laboratory tests (24, 52, and 72 weeks)	
 
Mean change from BL in         
 
Adiponectin
 
Leptin
 
hs-CRP
 
TNFα
 
 
 
Mean change from BL in         
 
eGFR
 
Urinary albumin/creatinine ratio
 
 
 

Patient-reported outcomes	

 
Change in SF-36v2 acute scores other than physical functioning (72 weeks)
 
	Mean change from BL in     role-physical score     bodily pain score     general health score     vitality score     social functioning score     role-emotional score     mental health score     physical component summary     mental component summary
Change in IWQOL-Lite-CT scores other than physical functioning (72 weeks)	
 
Mean change from BL in
 
physical score
 
psychosocial score
 
total score
 

 
Change in Patient Global Impression of Status (72 weeks)
 
	Shift of the ordinal response category from BL
To compare once-weekly tirzepatide (all doses combined) with placebo for participants with IGT at BL	
Delayed progression to T2DM at 72 weeks	Time to onset of T2DM during 72-week treatment period from BL

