# 4.9. Changes to Protocol-Planned Analyses

Efficacy analysis set for imaging data has been modified to accommodate the allowance of measurement schedule.

Added following exploratory objectives:

- Improvement of hyperuricemia (defined by uric acid ≤7.0 mg/dL).
- Improvement of hypertension: Diastolic blood pressure <80 mmHg or Systolic blood pressure <130 mmHg.
- Achievement of ALT ≤30 U/L.
- Changes in NAFLD fibrosis score.

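### SAP Table GPHZ.4.2 assigns the exploratory one-improvement endpoint to participants with 3 health problems instead of 1, so that objective has no analysis as written

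*SAP*

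**What the plan says.** The plan has three exploratory endpoints defined by the number of problems at baseline, whatever the BMI: 2 or 3 improved among participants with three problems, 2 improved among those with two, and 1 improved among those with one.

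The SAP's objectives table (Section 1.1.1) gives the last as "Achieved 1 improvement (only for participants with 1 defined obesity-related health problems". Protocol Section 3 has the same definition, and Protocol Section 8.1.3 words it as "Achieved 1 improvement (only for participants with 1 defined obesity-related health problem regardless of BMI at baseline".

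Table GPHZ.4.2 in SAP Section 4.4.3 turns these endpoints into analyses. Its last row has the criterion "Improvement in at 1 obesity related health problems" and the analysis set "Efficacy analysis set - participants with 3 defined obesity-related health problems". The row two above it, for 2 or 3 improvements, uses the same set. The row between them is correctly matched, with "Efficacy analysis set - participants with 2 defined obesity-related health problems". All three rows use the logistic model of SAP Section 4.3.2.2.

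SAP Section 4.9 lists the changes to protocol-planned analyses: one on imaging ("Efficacy analysis set for imaging data has been modified to accommodate the allowance of measurement schedule") and four added exploratory objectives. A change of population for this endpoint is not listed.

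**The concern.** The objectives need the analysis sets 3, 2, 1, and the table gives 3, 2, 3. The table is what a programmer works from. If it is followed, a stated objective goes unreported and a second analysis of the three-problem set takes its place.

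That second analysis is also hard to interpret. In a participant with three problems, improving exactly one is a worse result than improving two or three. An effective treatment can therefore lower the percentage counted as success.

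The plan does expect one-problem participants. Eligibility admits "A BMI of 35 kg/m² or greater and at least 1 obesity-related health problem", and the baseline summary in SAP Section 6.1.1 counts defined problems as 1, 2 or 3.

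**Working it through.** **Textual comparison.** The row has no stated figure to reproduce. The main finding needs no assumption.

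| Endpoint | Population in the objectives (Protocol 3 and 8.1.3, SAP 1.1.1) | Population in SAP Table GPHZ.4.2 |
|---|---|---|
| 2 or 3 improved | 3 problems | 3 problems |
| 2 improved | 2 problems | 2 problems |
| 1 improved | 1 problem | 3 problems |

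**Is the one-problem stratum analysed elsewhere?** No. The composite row uses the whole efficacy analysis set. The exploratory row for BMI of 35 or more mixes participants with one, two and three problems. The IGT, hyperlipidemia and NAFLD rows select on one condition whatever else is present. The Sankey diagram in SAP Section 4.7 is descriptive and is not meant for the study report.

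**Direction of the row as written.** The documents give no improvement rates per problem, so the rates below are assumptions. Let p be the probability that one problem improves, with the three problems independent.

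- Exactly 1 of 3: 3p(1−p)²
- At least 1 of 3: 1−(1−p)³
- Intended endpoint, 1 of 1: p

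For p = 0.25, exactly 1 is 3 × 0.25 × 0.5625 = 0.422 and at least 1 is 1 − 0.422 = 0.578 (0.75³ is also 0.422). For p = 0.75, exactly 1 is 3 × 0.75 × 0.0625 = 0.141 and at least 1 is 1 − 0.016 = 0.984.

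| Assumed p, placebo / tirzepatide | Exactly 1 of 3 | At least 1 of 3 | 1 of 1 |
|---|---|---|---|
| 0.25 / 0.75 | 42.2% / 14.1% (reversed) | 57.8% / 98.4% | 25% / 75% |
| 0.30 / 0.70 | 44.1% / 18.9% (reversed) | 65.7% / 97.3% | 30% / 70% |
| 0.10 / 0.50 | 24.3% / 37.5% (not reversed) | 27.1% / 87.5% | 10% / 50% |

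The function 3p(1−p)² has derivative 3(1−p)(1−3p), so it peaks at p = 1/3 and then falls. With placebo at 0.10, 0.20, 0.25 or 0.30, the comparison reverses once tirzepatide exceeds 0.646, 0.488, 0.424 or 0.368 respectively.

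**Correlated problems** (beta-binomial, within-participant correlation rho). For 0.25 against 0.70 the reversal persists but shrinks: 25.0% against 17.3% at rho 0.3, and 16.4% against 13.6% at rho 0.5. For 0.10 against 0.70 the result is reversed under independence (24.3% against 18.9%) but not at rho 0.3 (13.5% against 17.3%).

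**Model.** The Section 4.3.2.2 model has baseline IGT, hyperlipidemia and NAFLD as yes/no factors. In one-problem participants the three indicators sum to 1, so with the intercept they give rank 3 out of 4 columns. In three-problem participants all three are constant, and the rank is 1 out of 4. This assumes that the factors take the same measured baseline status that defines the set.

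**The case against.** The strongest reply is that this is a copying slip of small consequence. The right population stands in the same SAP and twice in the protocol, so programming review might catch it. The row is labelled exploratory, and the multiplicity scheme in SAP Section 2.1 covers only the co-primary hypotheses. That limits the weight of the point, but it does not make the table right.

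Second, the reversal depends on reading a garbled phrase literally. All three rows carry a stray *at*, while the composite row in the same table says "Improvement in at least 1 obesity related health problem". If *at least 1* was meant, nothing reverses. This stands, and so does the fact that the rates are assumed. The reversal is therefore a conditional, secondary consequence.

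Third, a reader might infer that participants with one problem are left out of the efficacy analysis. The documents do not support this. Those participants are in the composite row and in the row for their own condition, and those with BMI of 35 or more are also in the exploratory at-least-1 row. What is missing is their analysis as a separate stratum.

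Fourth, a reader might treat a single problem as confined to BMI of 35 or more. That is true of eligibility but not of the analysis set. SAP Section 4.4.1.2 determines baseline problems from measurements, and SAP Section 4.1 takes baseline as the last value collected at randomization. Triglycerides qualify a participant at Visits 1 and 2 and are measured again at Visit 3. A participant below 35 with two problems at screening can therefore have one at baseline. The objective itself applies regardless of BMI.

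**Conclusion.** The mismatch is certain from the text. As written, Table GPHZ.4.2 provides no analysis of the one-problem objective and uses the three-problem set twice.

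The documents do not support a claim that the row will show tirzepatide as inferior. It can favour placebo only if the criterion means exactly 1, and then only for some assumed rates: it does at 0.25 against 0.75, and it does not at 0.10 against 0.50. Under the at-least-1 reading the direction is right. Tirzepatide may then be close to 100% (98.4% in the first example), but placebo is not (57.8%), so the comparison would not be flattened. It would still not answer the objective.

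The impact is limited to one exploratory endpoint outside type I error control, and no primary or secondary conclusion depends on it. The documents do not give the expected number of one-problem participants, and the set may be small.

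**What to change.** In the last exploratory row of SAP Table GPHZ.4.2:

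- change the analysis set to the efficacy analysis set restricted to participants with 1 defined obesity-related health problem at baseline;
- change the criterion to improvement of that 1 health problem, which also removes the ambiguity of *at 1*.

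Add a note that the model for this row keeps only two of the three health-problem factors, because the three sum to 1 in this set.

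The cost is two table cells and one model note, with no change to data collection. It should be done before unblinding, since a later correction would look post hoc.

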Analysis Dataset	Analysis Type	Baseline	Postbaseline
SS	1.1) Treatment-Emergent Adverse Events	The baseline period is defined as the start of screening and ends prior to the first dose in of study treatment (typically at Week 0).	Starts after the first dose of study treatment and ends at the end of the study period (including off-drug follow up visit).
SS	1.2) Treatment-Emergent Abnormal Labs a , Vital Signs, and ECGs.	Baseline will include all scheduled and unscheduled measurements during the baseline period (Visit 1 to Visit 3)	Postbaseline will be defined as above (1.1). All scheduled and unscheduled measurements will be included.
SS	1.3) Change from Last Baseline to Week xx and to Last Postbaseline for Labs a ,Vital Signs, and ECGs.	The last scheduled and unscheduled non-missing assessment recorded during the baseline period defined above (1.2).	Postbaseline will be defined as above (1.1). Only scheduled visits will be included. The early discontinuation (ED) visits are considered scheduled visits.

Table GPHZ.4.1. Baseline and Postbaseline Definitions for Safety Analysis

Abbreviations: ECGs = electrocardiogram; SS = Safety Analysis Set.

For the primary and secondary efficacy endpoint analyses, data for participants with missing values at the 72-week visit will be imputed based on the method described in Section 4.3.2. Otherwise, missing values will not be explicitly imputed except for the parameters with only 1 postbaseline measure during the analysis period per schedule of activity, where last observation carried forward (LOCF) approach will be applied to impute the endpoint when ED measure is available.

End of study participation for a participant will be the earliest of date of death, date of withdrawal from further participation in the study, or date of safety follow-up visit (Visit 801). For participants considered to be lost-to-follow-up, end of study participation will be the date of lost-to-follow-up reported by the investigator. Participant data included in the database after the last date of study participation (including safety follow-up period) will be excluded from statistical analysis.

Statistical treatment comparisons will only be performed between tirzepatide 10 mg or 15 mg, and placebo. Since the trial is not adequately powered to detect difference among tirzepatide doses, comparisons among tirzepatide doses will not be performed unless otherwise specified.

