# 4.4.2.2. Main Analytical Approach for Categorical Measures with Only 1 Postbaseline Measure

For the percentage of participants achieving improvement criteria from randomization at 72 week visit, a logistic regression model will be used.

A logistic regression model with terms of treatment group, stratification factors: baseline IGT (yes or no); baseline hyperlipidemia (based on TG; yes or no); baseline NAFLD (yes or no) and sex (female, male) as fixed effects. Baseline measurement will be included as a covariate if appropriate.

For measurement with only 1 postbaseline measure during the analysis period per schedule of activity, where LOCF approach will be applied to impute the endpoint when ED measure is available.

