# 5. Sample Size Determination

Approximately, 348 participants will be screened to achieve 261 randomly assigned to study intervention (approximately 87 participants per intervention group).

The sample size determination assumes that evaluation of superiority of tirzepatide 10 mg and tirzepatide 15 mg to placebo will be conducted in parallel, each at a 2-sided significance level of 0.025 using a 2-sample t-test. Additionally, a difference of at least 11% mean body weight percentage reduction from randomization at 72 weeks for tirzepatide 10 mg and/or tirzepatide 15 mg compared with placebo, a common SD of 10%, and a dropout rate of 25% are assumed for statistical power calculations. Under the assumptions above, randomizing 261 participants in a 1:1:1 ratio to tirzepatide 10 mg, tirzepatide 15 mg, and placebo provides more than 90% power to demonstrate superiority of each tirzepatide dose to placebo.

The chosen sample size and randomization ratio also provides >90% power to establish superiority of tirzepatide 10-mg and/or tirzepatide 15-mg doses to placebo in terms of proportion of participants achieving at least 5% body weight reduction at 72 weeks, conducted in parallel using a Fisher's exact test, each at a 2-sided significance level of 0.025, assuming 25% of placebo-treated participants and 90% of tirzepatide-treated participants achieve the goal and a dropout rate of 25%.

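### Improvement of hypertension is sent to a single-measure Week 72 model although blood pressure is scheduled at 11 treatment visits, so early stoppers have no defined score

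*SAP*

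**What the plan says.** In SAP Section 4.4.3, Table GPHZ.4.4, the row for improvement of hypertension at 72 weeks reports "Proportion of participants who achieved improvements of hypertension" in the Efficacy Analysis Set (EAS), among participants hypertensive at baseline. The method is "Logistic model in Section 4.4.2.2". The row is marked as an exploratory addition to the protocol, and Section 4.9 lists it as such without explaining the choice of method.

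Section 4.4.2.2 is titled "Main Analytical Approach for Categorical Measures with Only 1 Postbaseline Measure". It fits a logistic model at the Week 72 visit. Its only missing-data provision reads "For measurement with only 1 postbaseline measure during the analysis period per schedule of activity, where LOCF approach will be applied to impute the endpoint", and it operates when an ED value exists.

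Section 4.1 sets the general rule. First, "For the primary and secondary efficacy endpoint analyses, data for participants with missing values at the 72-week visit will be imputed". Then, "Otherwise, missing values will not be explicitly imputed except for the parameters with only 1 postbaseline measure during the analysis period per schedule of activity".

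The hyperuricemia row of the same table uses "Longitudinal logistic model in Section 4.4.2.3". So do hyperlipidemia (Table GPHZ.4.2) and achievement of ALT ≤30 U/L (Section 4.7). Protocol Section 9.4.3.2 names longitudinal logistic regression for hyperlipidemia and the remaining categorical efficacy endpoints. It keeps the simpler logistic model for the obesity-related health problems and their composites.

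**The concern.** The cross-reference does not fit the measurement. Blood pressure is among the most frequently measured efficacy variables in the trial, yet its binary endpoint goes to the section for variables measured once. Uric acid, with three scheduled on-treatment samples, gets the repeated-measures model in a neighbouring row. Continuous blood pressure in the same table is analysed by MMRM, which uses all on-drug visits. The same readings would therefore count in full as a continuous outcome, but only at Week 72 once dichotomised.

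The mismatch matters because the missing-data rules depend on it. If none applies, the reported proportion describes participants still on drug at Week 72, and the on-drug readings of those who stopped are set aside. If the analyst assumes that the pointer brings the ED carry-forward with it, a different set of participants is scored. The SAP does not say which is meant.

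**Working it through.** **Inputs**
- Blood pressure visits: the vital-signs row of Protocol Table 2 (Section 1.3) marks Visits 4, 5, 6, 7, 8, 9, 12, 15, 16, 18 and 21, that is Weeks 4, 8, 12, 16, 20, 24, 36, 48, 52, 60 and 72. Count = 11, of which 10 precede Week 72.
- Off-schedule visits: Protocol Table 3 marks vital signs at ED and Visit 801, but not at Visit 99.
- EAS: excludes data later than 7 days after the last dose (SAP Table GPHZ.3.2).
- Arm size 87; planning assumption "a common SD of 10%, and a dropout rate of 25% are assumed" (SAP Section 5).
- Share hypertensive at baseline: not given in the documents; 50% to 70% is assumed.

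**Which rule scores an early stopper?**

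| Rule | Condition | Does hypertension meet it? |
|---|---|---|
| Week 72 imputation (4.1, pointing to 4.3.2) | Primary or secondary endpoint | No, exploratory |
| ED carry-forward (4.1, 4.4.2.2) | One scheduled post-baseline measure | No, 11 scheduled |
| Observed Week 72 value | Within last dose + 7 days | No, if drug was stopped early |

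Nothing in the text supplies a score. A participant who stops drug but stays in the study may still have blood pressure taken at Week 72, but that reading falls outside the EAS.

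**The plan's own figure.** The SAP states no power for this endpoint. For the co-primary endpoints it states more than 90%. With 87 × 0.75 = 65.25, taken as 65 per arm, power at two-sided 0.025 exceeds 0.999 for the t-test (difference 11, SD 10) and for Fisher's exact test (25% versus 90%). The stated figure is reproduced.

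**Precision.** If 25% are unscored, the standard error ratio is √(87 / 65.25) = √1.333 = 1.155. The ratio is the same in any subset losing the same fraction. It is a ceiling, because a longitudinal model recovers only part of the missing Week 72 information.

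**Numbers per arm**
- 50% hypertensive: 87 × 0.5 = 43.5, of whom 43.5 × 0.25 = 10.9 are unscored.
- 70% hypertensive: 87 × 0.7 = 60.9, of whom 60.9 × 0.25 = 15.2 are unscored.

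That is about 11 to 15 of 44 to 61 per arm.

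**Illustrative simulation** (1,000,000 per arm; every input assumed). Baseline systolic pressure is 130 + |N(0, 12)|. Week 72 change is N(−3, 12) on placebo and N(−11, 12) on tirzepatide. The interim change has the same mean and SD and correlates 0.6 with the Week 72 change. Dropout is 25% in each arm, logistic in interim systolic pressure. Response is systolic pressure below 130.

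| Dropout slope per mmHg | Placebo completers | Tirzepatide completers | Difference (points) |
|---|---|---|---|
| 0 (no selection) | 33% | 55% | about 22.5 |
| 0.03 | 35% | 58% | 23.1 |
| 0.06 | 37% | 60% | 23.5 |

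Differences are computed before rounding. Each arm's rate rises by 2 to 5 points; the contrast rises by 0.6 to 1.0.

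**The case against.** The SAP never says that early stoppers are dropped. The row adopts 4.4.2.2, whose one missing-data rule carries an ED value forward, and blood pressure is taken at ED. A programmer following the pointer could use that reading if it fell within 7 days of the last dose. This stands as a plausible reading, but it contradicts the rule's own condition; that the row has two readings is itself part of the problem.

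A reader might infer that the treatment comparison is materially biased. The working does not support that: with equal dropout the contrast hardly moves. The simulation also scores systolic pressure only, whereas the SAP counts response on either systolic or diastolic pressure, so its rates do not describe the actual endpoint. Unequal dropout was not examined.

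A reader might also take 25% as the share who will stop drug. It is a planning dropout rate for the body-weight endpoints, not an estimate of drug discontinuation or of losses among hypertensive participants.

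Nor do the documents show a clear breach of the efficacy estimand. SAP Section 1.1.2.1 defines it for body weight, and Section 4.4.3 extends it to secondary objectives; this endpoint is exploratory. Continuous blood pressure is still analysed by MMRM, so the trial's main assessment of blood pressure keeps the early stoppers' readings.

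Finally, changing the pointer alone is not enough. Section 4.4.2.3 names no estimation method, covariance structure or convergence fallback. It fixes baseline body weight as covariate, where 4.4.2.2 allows the baseline measurement. This objection stands and shapes the fix.

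**Conclusion.** The concern holds as a minor, specific mismatch. The method assigned to this row is built for single-measure variables, blood pressure is measured at 11 treatment visits, and on a literal reading no missing-data rule covers an early stopper. The choice also departs from Protocol Section 9.4.3.2 and from how the SAP treats hyperuricemia, hyperlipidemia and ALT.

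The costs are lost precision (standard error at most about 15% larger if 25% are unscored), per-arm response rates that may be overstated if stopping is related to on-drug pressure, and an analysis that can be run two ways. The precision figure rests on applying the planning dropout rate to the hypertensive subset; the participant counts also rest on the assumed 50% to 70% prevalence. The shift of about 1 point or less in the contrast rests on equal dropout and a systolic-only model. The endpoint is exploratory and unpowered, so primary conclusions are unaffected.

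**What to change.** In Table GPHZ.4.4, change the method for improvement of hypertension from Section 4.4.2.2 to the longitudinal logistic model in Section 4.4.2.3. Use the scheduled on-drug blood pressure visits and report the Week 72 contrast. Name a fallback to Weeks 24, 52 and 72, the reporting times already used for continuous blood pressure, in case 11 binary visits do not converge.

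Add a sentence to Section 4.4.2.3 saying that the model is fitted by a likelihood method, so that early stopping is handled under missing at random; an ordinary GEE fit would not secure this. State also whether baseline blood pressure enters as a covariate. If the sponsor prefers to keep 4.4.2.2, the minimum is to write down the missing-data rule for this row.

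The cost is one table entry, a sentence or two of model text that will also govern the other endpoints using 4.4.2.3, and possibly some convergence work. No new data are needed.
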